### **ONSITE VISITS (ONCE WRITTEN APPROVAL FROM ACOS /R&D FOR RESUMING ON-SITE VISITS IS PROVIDED)**

MRI scans (2b and 13b) and treatment-based visits (3-12) will be conducted onsite at the UCSD fMRI Center and at VA San Diego Building 23, respectively, with increased safety measures.

#### **Section 9.4 Devices**

**9.4) For each research device, state the status of the device, the PI's determination as to whether the device is a significant or non-significant risk device, and provide justification for this determination. A copy of determinations from the FDA should be attached. - Also, for investigational devices describe how and by whom the device will be received, stored, secured and dispensed.**

Device: TMS Magpro Magventure, previously approved through engineering department for research studies H130281, H160047

rTMS is currently FDA approved for treating major depression and single pulse TMS is approved for treating migraine headaches. This treatment technology has an excellent safety track record when used under the safety guideline established in 1998 [74]. A recent study demonstrated that unilateral rTMS as well as bilateral combined rTMS revealed no detrimental effects on cognition in comparison to the sham group 3 months after the treatment [2]. On the other hand, rTMS is found to have mild beneficial cognitive effects [24]. In lack of any major breakthrough in establishing other effective long-term treatment regimen for MTBI-HA and co-morbidities, this safety track record and potential benefits associated with rTMS supports the feasibility of the proposed study in a rapidly growing patient population with debilitating symptoms.

The PI believes that this device does not meet the definition for a significant risk device (SR) and therefore falls into the non-significant risk (NSR) device classification under the current FDA guidelines:

According to the FDA, under 21 CFR 812.3(m), an SR device means an investigational device that:

- Is intended as an implant and presents a potential for serious risk to the health, safety, or welfare of a subject;
- Is purported or represented to be for use supporting or sustaining human life and presents a potential for serious risk to the health, safety, or welfare of a subject;
- Is for a use of substantial importance in diagnosing, curing, mitigating, or treating disease, or otherwise preventing impairment of human health and presents a potential for serious risk to the health, safety, or welfare of a subject; or
- Otherwise presents a potential for serious risk to the health, safety, or welfare of a subject.

#### FDA DOCUMENTS

MagPro rTMS: K091940 & K061645

MEDOC TSA II NeuroSensory Analyzer: k010981 & TSA-II\_Brochure (FDA Approval)

Request for NSR justification & abbreviated IDE designation

MagPro rTMS: This device study is one that does not meet the definition for an SR device study and therefore falls into the NSR classification under the current FDA

The device has been used by the PI in 5-6 approved studies, the latest one being protocol #H160047.

## Section 9.8 Questionnaires & Surveys

**9.8) Provide the name and a reference for questionnaires/surveys that are standard or identify them here and attach a copy of the questionnaire/survey. Questionnaires or surveys that are not clinical standard references must be uploaded. Reference the help link for additional information related to surveys administered to VA personnel and approved platforms for web-based surveys.**

Questionnaires & Surveys (copies attached):

- 1.Numerical Pain Rating Scale (NPRS): scale that ranges from no pain to worst possible pain.
- 2.Headache Log: Daily log to report if they have a persistent (non-stop, 24/7) headache over the last 24 hours and rate the average intensity of the headache on a 0-10 Numerical Rating Scale (NRS). In addition, they will be asked to report the duration and intensity of any debilitating headache exacerbations, which completely incapacitate their daily functions.
- 3.Neurobehavioral Symptoms Inventory (NSI): A self-report on the severity of each symptom is measured using a 5-item scale. It asks the subjects to indicate the extent to which each symptom has disturbed them.
- 4.Headache Impact Test (HIT-6): Measures how impact headaches affect the individual's ability to function in different domains.
- 5.Short Form Health Survey-36: A patient-reported survey of patient health. It is a measure of health status and quality of life in regards to eight main areas: vitality, physical functioning, bodily pain, health perceptions, physical, emotional, and social role functioning and mental health.
- 6.Clinician-Administered PTSD Scale (CAPS-5): A 30-item structured interview that can be used to diagnose PTSD and associated symptoms.
- 7.Conner's Continuous Performance Test (CPT II): A widely used test of sustained attention using a computer program. It provides a detailed picture of response time, impulsivity, and attentiveness.
- 8.Hopkins Verbal Learning Test: Hopkins Verbal Learning Test: This is a verbal list learning measure with multiple equivalent forms to minimize practice effects in repeat testing. It provides information about learning acquisition as well as short and long delayed recall. It has been used successfully in previous trials of rTMS.
- 9.Trial Making Test A and B: This is a widely used test of executive functioning. It consists of an attention/processing speed condition (connecting numbers in order quickly) followed by a more complex sequencing task (alternating between numbers and letters).
- 10.Stroop Test: Participants must inhibit a pre-potent response to provide the required response on this test of inhibition.
11. Hamilton Rating Scale for Depression (HRSD: This scale is a well-established questionnaire which consists of 21 questions and rates the severity of symptoms observed in depression such as low mood, insomnia, agitation, anxiety and weight loss. The scale is frequently used in TBI related studies for assessing the severity of depression.
12. Brief Pain Inventory: Assesses the intensity of physical pain and the levels of interference using a numerical rating scale (1 to 10).
13. Eye-Tracker Assessment: assesses eye movement during a test to learn more about attention in this population.

## Section 9.9 Data Safety Monitoring Board or Plan

**9.9) Provide a Data Safety Monitoring Plan (DSMP) or the details of a Data Safety Monitoring Board; if a**

**written plan is available, attach a copy of the plan to the submission form.**

The DSMB will review all unanticipated problems involving risk to study subjects, serious adverse events, and all subject deaths associated with the protocol, and provide an unbiased written report of the event within 10 calendar days. The DSMB will provide an independent evaluation of adverse events and unanticipated problems involving risk to subjects to the Human Subject Protection Committee. The DSMB will comment on the outcomes, adverse events, and relationship of the events to the protocol. The DSMB will indicate whether they concur with the details of the report provided by the PI. The DSMB promptly reports discrepancies or problems to the Committee. They have the authority to stop a research study in progress, remove individual volunteers from a study, and take whatever steps will be necessary to protect the safety and well being of research subjects until the IRB can assess the report. The members of the DSMB for this proposal will comprise of a pain specialist, a clinical psychologist and a biostatistician who will be independent of the investigative team and possess sufficient educational and professional experience to serve as the subjects' advocate. The members of DSMB also have no apparent conflicts of interest.

The DSMB members include:

[name]., Ph.D. (pain specialist)

[name] is an Assistant Professor of Anesthesiology at UC San Diego, School of Medicine, with sub-specialty training in pain management.

[name]. (psychologist)

[name] is a Professor of Psychiatry at UC San Diego, School of Medicine. He is the Associate Director of the Neuropsychiatry and Behavioral Medicine Service at the UCSD-Medical Center. He also serves as the Chief Supervising psychologist at UCSD-Medical Center and is a member of Neuropsychological Associates.

[name], MA, MBBChir, MSc, FRCPC (Neurologist, rTMS expert)

[name] is a Professor of Neurology at the University of Toronto. He is an expert of rTMS in both clinical application and basic science research.

[name]. (Biostatistician)

[name] is the current Director of Biostatistics at the UC San Diego, Clinical and Translational Research Institute. She is experienced in analyzing data from large-scale clinical trials.

The members of the DSMB will meet on an as needed basis. Given the geographical location difference and lack of other local experts in rTMS, [name] will join the board meeting via teleconference. If a serious AE or UPR occur, then the members of the DSMB will be contacted by the PI and a meeting will be set up to address the situation as soon as possible.

The members of the DSMB will not have access to the subject identifying information when reviewing adverse events, and will only be presented with the unique study number.

#### **SAFETY MEASURES IN RESPONSE TO COVID-19**

The following safety measures will be used to reduce risk and compliance is to be documented at each On-site visit: screening for COVID-19, PPE, hand washing, reduced staff and scheduling, and sanitization of equipment. A checklist will be used to document that all safety measures are followed and has been attached to the protocol revision.

COVID-19 Screening:

During consent/screening call, subjects will be screened for COVID-19 with the questions provided by the research office to be enrolled in the study:

1. Do you have:

- a. A Fever
- b. New or worsening cough or shortness of breath
- c. Flu-like symptoms

2. Have you or a close contact travelled to an area with community transmission of COVID-19 within the past 21 days? For example, including but not limited to Europe, the middle east, Asia, and/or areas of the United States with significant spread of COVID 19, such as Washington State, New York, Massachusetts and Northern California

3. Have you been in close contact with someone, including health care workers, confirmed to have the coronavirus disease?

Subjects who answer "no" to all questions will be enrolled in the study. Should a subject answer

that they have had symptoms of COVID-19, they will be advised to come into the hospital for testing and a negative test (or confirmation that they are no longer positive) will be required before enrollment.

1-2 days before an on-site visit, subject will be contacted via phone call to screen for COVID symptoms. On arrival at site, screening will be conducted at the entrance of the hospital and when entering the lab for their appointment. Subjects will also be required to have their temperatures check with an IR thermometer. If all symptomology is negative, subjects will be enrolled/allowed to continue with their visit.

If a subject indicates moderate to severe symptoms, subjects will be required to report to the COVID-19 triage for testing. If a subject indicates mid symptoms, such as low fever or only one symptom, and the VA is unable to provide testing, subjects will be asked to stay/return home and will be provided with a COVID-19 home testing kit. If positive results, subjects will be asked to stay home for at least 14 days and seek medical attention through their primary care provider. Subjects may continue with the study after 2 weeks of quarantine or with note from their care provider that they are no longer positive for COVID-19 and under the discretion of the PI. If the subject is unable to meet the study timelines due to COVID-19 the subject may be withdrawn from the study under the discretion of the PI.

Any staff in contact with the subjects will be asked to return home, monitor for COVID-19 symptomology, and tested for COVID-19 with home kit. If test is positive and staff shows symptoms, medical care should be sought and staff are to stay home until they are healthy. If test is positive but employee is asymptomatic, staff should stay quarantined for 2 weeks. If the test is negative, staff should stay at home for 2-5 days to ensure before returning to work as a safety precaution. Staff will also be screened by the hospital when reporting to duty each day.

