#### Research Design:

A total of 200 will be consented and 128 (64 per group, accounted for 36% dropout rate) patients will be randomized to be stratified based on their injury mechanisms (blast, non-blast) and headache severities (mild, moderate, severe) and enrolled over 6 years from VASDHS, and Naval Medical Center San Diego (MNCS). Patients meeting study enrollment criteria will be randomized into one of the two study groups (A&B) based on their mechanisms of injury, gender, severity of headache, and past failed therapies for their headache. The overall study duration for each subject is about 14 weeks developed into three phases according to the following schedule:

- 1) PRE-TREATMENT PHASE (weeks 1-2) consists of Visit 1 (Screening Visit) and Visit 2 (Pre-treatment Assessments);
- 2) TREATMENT PHASE (week 3-4) consists of Visits 3-12 (Neuronavigation guided rTMS consisting of 10 weekday treatments at  $>24$  and  $< 72$  hours apart, weekends excluded, maximum 5 weeks for treatment completion) rTMS will take place in Building 23 Room 105 at the VASDHS; and

3) POST-TREATMENT PHASE (week 5-14) consists of two initial weekly visits (Visits 13&14) and two additional biweekly visits (Visits 15&16) and one monthly visit (Visit 17).

Brain anatomical and functional MRI will be performed within 72 hours after Visits 2 and 13. Subjects will be required to fill out headache diary between assessment visits. Headache assessments along with quality of life, mood and functions assessments will be carried out at Visits 1,2, and 13--17. This frequency of treatment and duration of follow-up is in line with recently published rTMS articles related to TBI, headache and pain, and also in accordance with the 3-month post treatment initiation follow-up guideline /recommendation [32; 55; 80].

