#### **A) Headache assessment (specific aim #1, see Appendix 6b for assessment samples)**

Due to the persistent and debilitating nature of MTBI-HA, two areas of headache characteristics: **1) Persistent Daily Headache**; and **2) Debilitating Headache Exacerbation** will be especially assessed during the study in addition to more conventional headache assessments. Patients will be provided with a daily headache diary, which they will fill out every evening during the study between-visit periods (B1-B6). In the diary, they will report if they have a persistent (non-stop, 24/7) headache over the last 24 hours and rate the average intensity of the headache on a 0-10 Numerical Rating Scale (NRS). In addition, they will be asked to report the duration and intensity of any debilitating headache exacerbations, which completely incapacitate their daily functions.

For persistent headache, the intensity of the headache from the diary will be averaged (sum of headache NRS scores/number of days) as between-visit persistent headache severity assessment. Should the headache becomes sporadic after the study rTMS interventions, the subjects will then record the total number hours of headaches over the previous 24 hours and the average intensity of the headache, they will still record the duration and intensity of any debilitating headaches. The occurrence of lingering persistent daily headaches and average intensity of daily headaches will be recorded [38; 43].

For debilitating headache exacerbation, a composite score will be generated by multiplying the average duration (hours/episode) of the headache exacerbation by the average frequency (episodes per day) and the average intensity (NRS) of the headache exacerbation [38; 45] .

Aside from assessing the daily intensity and exacerbation pattern of MTBI-HA, additional assessments for the impact of headaches on the patients' quality of life will include:

1) the **Headache Impact Test (HIT-6)** which will assess the impact of headaches on the subjects' ability to function on the job, at school, at home and in social situations [66; 79];

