## **VI). Process of randomization and treatment double blinding**

The un-blinded study biostatistician, [name], will create a list of patient identification numbers with randomized treatment assignments (A = Active/Real, B = Sham) using the SPSS software prior to the start of the study subject recruitment. Blocked randomization will be used with random block size of 3 or 6. Separate lists (up to 12) of replacement patient identification numbers will also be created so that replacement patients are assigned the same treatment as patients they are replacing. Patients will be randomized to study treatment groups in a 1:1 ratio. [name] will be contacted by the study coordinator with subjects' unique master ID number (sequential number, independent from any protected health information or any other identification source) and their descriptive information. After a subject signs the study consent, the study coordinator will be provided with that subject's randomization code. A minimization random assignment procedure will be used to match subjects on four variables: 1) mechanisms of injury; 2) gender; 3) severity of headache, and 4) past failed therapies for their headache. The minimization random assignment procedure aims to obtain equal numbers of subjects at the different levels of each matching variable. In contrast to stratified randomization, which aims for equal numbers of subjects in each treatment for every possible combination of the interested variables, the minimization method restricts its aim to equalizing treatment numbers at the different levels of each variable taken separately [20; 77]. Essential for this study, the procedure allows sequential assignment of subjects. This method has been shown to be superior to both simple and

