stratified randomization in producing a balance for separate prognostic variables, particularly when the number of strata is large in comparison with the number of subjects. In addition to violations of inclusion and exclusion criteria, reasons for randomization failure include major protocol deviation, lost to follow-up, voluntary withdrawal, and study termination will be communicated with [name]. The randomization code will be input into the TMS software in guiding the orientation of the Cool B65 A/P coil for each subject based on a built-in gravity sensor mechanism. This method of double blinding with the use of Cool B65 A/P coil as recommended in a recent guideline for rTMS in pain/headache related studies [32] will blind both the subjects and the investigators to the study treatments.

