17	Post-TX 12 Week Assessments	Telehealth	Within 84-93 days of V11	Assessments and Questionnaires

Table 1: Summary of Study Design in Response to COVID-19

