#### Reduced Staff and Scheduling

On-site staff will be limited to 2 study coordinator and the PI and in-person interactions with subjects will be limited to one study coordinator and the PI. Only one subject will be enrolled per week, at least a 30-minute window between each appointment, and only 2 subjects will be in the treatment phase at a given time with alternating treatment schedules.

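### The COVID-19 clause lets the PI end study participation, not only rTMS, and nothing in the protocol continues outcome collection after an incomplete course, although it could be done remotely

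*Combined protocol and SAP*

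**What the plan says.** The section on safety measures in response to COVID-19 asks a patient who tests positive to stay at home for at least 14 days. It then offers a way back: "Subjects may continue with the study after 2 weeks of quarantine", or with a care provider's note, at the PI's discretion. The next sentence covers the patient who is "unable to meet the study timelines due to COVID-19 the subject may be withdrawn from the study under the discretion of the PI".

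The treatment timelines are in Research Design and in the COVID-19 visit table. There are ten sessions, more than 24 and less than 72 hours apart, with "weekends excluded, maximum 5 weeks for treatment completion". Under Reduced Staff and Scheduling, "only 2 subjects will be in the treatment phase at a given time with alternating treatment schedules".

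The primary outcome is the diary-based daily headache score over periods B1-B6. Patients fill in the diary every evening and, under the COVID-19 revision, return it by portal or fax. Visits 13a and 14-17 are telehealth; only the 13b MRI is on site. The follow-up windows count from a treatment visit. Visit 17, for example, falls "Within 84-93 days of V11".

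The randomization section says that "reasons for randomization failure include major protocol deviation, lost to follow-up, voluntary withdrawal, and study termination" will be reported to the biostatistician, and it prepares lists so that "replacement patients are assigned the same treatment as patients they are replacing".

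**The concern.** Stopping rTMS and ending follow-up are separate events, and the COVID-19 clause merges them. An infection can make it impossible to attend ten sessions within the permitted spacing. It does not by itself stop a patient from filling in a diary at home, answering a weekly call or joining a video visit. If such a patient is withdrawn from the study, later primary outcome data are lost although they could have been collected.

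A patient who stops before V11 has a further problem: the visit windows have no anchor date. Even a coordinator who wanted to continue would have no schedule to follow.

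What is at stake is mainly retained randomized data. Bias would arise if the patients withdrawn differed between arms in number or in later headache, and the documents give neither quantity.

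**Working it through.** **Is there any text that continues follow-up?** The nearest provisions, taken one by one:

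- Assessment Based Visits: the diary continues for the course of the study, which a withdrawn patient has left.
- Weekly Phone Assessment (two entries): calls start after the treatment phase or after the one-week post-treatment assessment, and run to study completion. Neither mentions an incomplete course.
- COVID-19 visit table: the post-treatment windows count from V11, which is the ninth of the ten sessions (Visits 3-12).
- Randomization section: it provides replacements but does not address follow-up of the patient replaced.
- Statistical Analysis for Hypothesis #1: patients terminated early enter the mixed model with the data they have, and pattern-mixture models are planned. Nothing there concerns further collection.

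**Can a quarantine put a patient outside the timelines?**

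- Spacing: 14 days × 24 h = 336 h. If the two weekends are excluded, 336 − 96 = 240 h. Both exceed 72 h, so a quarantine between sessions breaches the spacing limit.
- Five-week maximum: 5 × 7 = 35 days. The session pace is an assumption. From a Monday start, with the same pace kept after the gap:

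| Pace | Course (days) | Plus 14 days | Within 35? |
|---|---|---|---|
| Consecutive weekdays | 12 | 26 | Yes |
| Mon/Wed/Fri | 22 | 36 | No |
| Alternate weekdays | 25 | 39 | No |

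- The last row depends on when the gap falls. Alternate-weekday sessions are on days 1, 3, 5, 9, 11, 15, 17, 19, 23 and 25. A patient interrupted after session 5 resumes on day 15 + 14 = 29 and, on consecutive weekdays, has the last five sessions on days 29-33, which is within 35. After session 6, resumption is on day 17 + 14 = 31, and the last four sessions fall on days 31, 32, 33 and 36, which is not.

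**What does one patient who leaves during treatment lose?**

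- Diary: seven assessment visits (1, 2, 13-17) give six between-visit periods. This mapping of B1-B6 is inferred. B2 runs from Visit 2 to Visit 13, so B3-B6 are lost (4/6 = 67%), plus the rest of B2.
- Post-treatment diary days: 12 × 7 = 84 on the COVID-19 schedule, or 10 × 7 = 70 on the Research Design schedule.
- Assessments: five of the six at Visits 2 and 13-17.
- Share of the trial: 128 × 4 = 512 patient-periods in B3-B6. One patient is 4/512 = 0.8%. With at most two patients in treatment at a time, one site interruption affects at most 8/512 = 1.6% through patients in treatment.

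**How many such patients?** Not stated. The expected 10-20% dropout (about 13 to 26 of 128) is not split into stopping treatment and refusing follow-up. No bias or power figure is claimed, and the planned 85% power does not enter the argument.

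**The case against.** The strongest reply is that COVID-19 is an external event with no stated link to arm or headache, and that the clause is applied at discretion by a PI who is blinded, as are patients and coordinator. For losses of that kind, a mixed model on available data with a pattern-mixture check is a reasonable safeguard. The plan already allows for 10-20% dropout. The coordinator is told to head off avoidable dropout, and payments are set partly to aid retention. Each patient is under 1% of the later patient-periods.

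Much of this stands. It makes differential withdrawal less likely and keeps the point to one of retained data. It does not supply the missing rule. The models cannot replace outcomes never collected. The planned comparison of dropouts with completers uses baseline data only, so it cannot show whether missingness depends on later headache. The retention measures do not say what happens after the PI ends participation.

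Several stronger readings are tempting but unsupported:

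- A reader might infer that every quarantined patient is withdrawn. The clause is permissive and follows a route back.
- A reader might infer that a 14-day gap always breaks the 5-week maximum. That depends on pace and timing, as the dates show.
- A reader might infer that replaced patients leave the analysis. The randomization section does not say so.
- A reader might take the instruction under Protection from Risk, on stopping the study for excessive discomfort, as ending follow-up. It may mean only the stimulation.
- A reader might treat the effect at the last time point as the estimand. The power section uses it to define an effect size; inference is from a saturated treatment-by-time model, to which an early leaver still contributes B1 and any observed B2.

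**Conclusion.** The point holds in a limited form. The clause allows withdrawal from the study where discontinuing treatment would be enough, and the available text does not continue outcomes after an incomplete course, although the primary diary, the calls and Visits 13a and 14-17 need no attendance. The avoidable loss per patient who leaves during treatment is about 4 of 6 diary periods and 5 of 6 assessments. The 13b MRI, and headache M-VAS ratings taken on site, would not be recovered.

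Bias is possible but not shown, and the total effect on the trial cannot be sized because the number of such patients is unknown. The finding rests on the inferred B1-B6 mapping and on the text available; the consent pages and the COVID-19 checklist were not seen and may say more. It concerns only patients under the COVID-19 revision. This is a cheap improvement worth making, since follow-up not collected at the time cannot be recovered later. It is not a defect that invalidates the analysis.

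**What to change.** In the COVID-19 safety section, for randomized patients, replace withdrawal from the study with the following rule. Study treatment may be discontinued, or not started, at the PI's discretion. The daily diary, weekly calls and telehealth Visits 13a and 14-17 then continue unless the patient withdraws consent for follow-up, is lost to follow-up, or is removed for safety by the PI or the DSMB. The route back after quarantine stays as it is.

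The protocol sets no planned V11 date, so add one. Project V11 at the first treatment session from the patient's booked session schedule or, if no session was given, from the scheduled start of treatment. Time the follow-up visits from that date, which keeps measurement occasions aligned in the treatment-by-time model.

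State that the patient stays in the randomized arm in the primary analysis even if a replacement is enrolled. Record the reason for stopping treatment separately from the reason for ending follow-up.

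The cost is amendment wording, some coordinator time, and up to 5 × $50 = $250 in assessment payments per patient who would otherwise have left (Section 20). The estimated effect may be smaller because patients with partial courses are included.
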